**Trial Outcomes:**

The primary outcome is to investigate patient adherence to the regular use of activity trackers to monitor and adjust daily physical activity levels during the course of a standard pulmonary rehabilitation programme (16 sessions) that includes behavioral modification consultancy sessions to adopt an active lifestyle.

Secondary outcomes include:

- Change In physical activity at 9 weeks;
- Change in hospital anxiety and depression score at 9 weeks;
- Change in 6MWT at 9 weeks
- Change in QOL at 9 weeks

## **Assessment Procedures (Pre & Post):**

### *Pulmonary function:*

Pulmonary function assessment will be performed before and after completion of the PR program. The assessment will include comprehensive evaluation for the determination of Forced Expiratory Volume at the 1st second (FEV1) and Forced Vital Capacity (FVC) (Table 1).

### *Functional capacity:*

The six-minute walk test (6 MWT) will be performed according to the instructions of the American Thoracic Society [14], in order to assess the functional capacity of the patients. Intensity of dyspnoea and leg discomfort will be assessed by the modified Borg scale, whereas cardiac frequency (fc), and oxygen saturation will be recorded every min and at the end of 6 MWT. The 6 MWT will be performed within 1 week before and one week after the end of the rehabilitation program (Table 1).

### *Daily physical activity:*

Assessment of Daily Physical Activity will be performed one week before starting the PR program and one week after the completion of the PR program (9th week) using a triaxial accelometer (Actigraph GT3X; Actigraph LLC, Pensacola, FL, USA). Patients will be asked to wear the activity monitor during wakefulness for 7 consecutive days. Daily step count will be performed over 7 days, with at least 3 acceptable days' data, excluding days with less than 8 hours of wear time (Table 1).

### *Health-related Quality of Life:*

[figure not shown]
Quality of Life (QoL) will be assessed at the onset and following completion of the PR program. Patients will be asked to complete different questionnaires in order to evaluate their emotional condition and symptoms. The assessment of QoL will include 2 different questionnaires namely: Hospital Anxiety and Depression Score (HADS), and the St George's Respiratory Questionnaire (StGRQ)). The questionnaires will be administered within 1 week before and within 1 week after the end of the rehabilitation programme.

## **Statistical plan**

[figure not shown]
Statistical analyses will be supported by standard statistical software (e.g. SPSS, SAS) as required. This is a feasibility study and key outcomes of interest relate to adherence, attendance and drop out rather than clinical outcomes. However, clinical outcome data (steps/day) will be collected and reported to help inform a future randomized controlled trial. Feasibility data will be summarized using standard descriptive statistics, depending on the level of the data (e.g. mean, median, standard deviation, range). Baseline characteristics between groups will be assessed by t-tests for independent samples. Differences between groups across different time points will be assessed by a two-way ANOVA with repeated measures followed by appropriate post-hoc analysis. The Level of significance is set at  $p < 0.05$ .

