**Study population:**

We will recruit 40 stable COPD patients.

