**Planned interventions:**

Following confirmation of eligibility, informed consent (Appendix 1) and baseline assessment (Table 1), 40 patients will be randomised to: 1) an 8-week pulmonary rehabilitation programme according to British Thoracic Society (BTS) standards [11] or 2) 8 weeks of standard pulmonary rehabilitation alongside [10] physical activity promotion [6], (Fig. 1). Randomisation will be performed independently, with 1:1 allocation using stratification, variables: HADS (8 or above) and 6MWT (above or below 350m) [6] & [12], (Fig. 2).

*Standard Care Pulmonary rehabilitation;*

*Exercise Sessions:*

All patients will attend a group programme running twice weekly for 8 weeks (16 sessions) for approximately 50 minutes of exercise and 20 minutes of education or relaxation. The exercises include an individualised programme of aerobic (cycling and walking) and strengthening exercises were each patient would be progressed at each session as able.

*Cognitive behavioural modification (CBM):*

CBM strategies are part of standard care pulmonary rehabilitation at the Royal Victoria Infirmary. Made up of four elements: behaviour, cognition/thoughts, feelings/emotions, and physical sensations [13]. A number of techniques will be used to aid symptoms of anxiety and depression including; education on anxiety and depression and COPD, distraction techniques, breathing control and relaxation and rating achievement/pleasure of physical activities [10] (Figure 1). CBM will be administered once at study entry (week 1 for 45 min session), and three times during weeks 2, 3 and 4 for 30 min each time.

*Physical activity Promotion:*

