**Table 1: Assessment of variables prior to and following the rehabilitation programme**

Visit number (Assessments)	1	2	3	4
	Week 0	Week 1	Week 9	Week 10
Inclusion/Exclusion criteria	x			
Information & Informed consent	x			
Physical examination	x			
mMRC evaluation	x			
Current medication review	x			
Pulmonary Function Assessment		x		
Heart Function Assessment (resting ECG)		x		
BMI (body composition)		x		x
Oximetry & Blood Pressure		x		
6 Minute Walk Test		x		x
Daily Physical Activity Assessment	x		x	x
Quality of Life Assessment		x		x

**Figure 1: Study design** . PA: physical activity; CBM: cognitive behavioural modification, 6MWT: 6-min walk test, HADS: Hospital anxiety and depressions score, StGRQ: St’Georges Respiratory questionnaire.

**Figure 2: Consort Diagram.** PR: pulmonary rehabilitation, CBM: cognitive behavioural modification, PA: Physical activity promotion.

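### The repeated-measures ANOVA fixed for the clinical outcomes is valid but usually less precise than a baseline-adjusted ANCOVA on the same data

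*Protocol*

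**What the plan says.** The Statistical plan names one method for comparing the arms over time: "Differences between groups across different time points will be assessed by a two-way ANOVA with repeated measures followed by appropriate post-hoc analysis". It names no baseline covariate. The same section treats adherence, attendance and retention as the main interest, and says steps/day will be reported to support the design of a later randomised trial.

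Trial Outcomes lists the secondary outcomes as changes, for example "Change in 6MWT at 9 weeks". The assessment sections describe one measurement on each side of the programme:

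- Functional capacity: "The 6 MWT will be performed within 1 week before and one week after the end of the rehabilitation program".
- Health-related Quality of Life (HADS and StGRQ): "The questionnaires will be administered within 1 week before and within 1 week after the end of the rehabilitation programme".
- Daily physical activity, for steps/day, reads: "Assessment of Daily Physical Activity will be performed one week before starting the PR program and one week after the completion of the PR program".

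Table 1 is less clear for the last of these. Its row "Daily Physical Activity Assessment" is marked at weeks 0, 9 and 10.

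On size and allocation, Study population states: "We will recruit 40 stable COPD patients". Planned interventions gives 1:1 allocation, so 20 per arm, "using stratification, variables: HADS (8 or above) and 6MWT (above or below 350m").

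**The concern.** The outcomes are defined as change, so the term of the ANOVA that carries the treatment effect is group-by-time. With one value before and one after, that term is the comparison of mean change between arms. Comparing changes is the same as adjusting for baseline with a slope of exactly 1. When the true slope is below 1, as it is with equal SDs and imperfect correlation, this over-corrects for baseline and adds noise. ANCOVA estimates the slope and removes that noise without any further measurement.

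What is at stake is the width of the interval around the between-arm differences. With about 20 per arm those intervals will be wide in any case. The steps/day result is meant to inform a later trial, so avoidable width is worth removing. Bias, type I error and the primary adherence outcome are not at issue.

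**Working it through.** **Inputs from the protocol.** 40 patients, 1:1, so 20 per arm; one pre and one post value per outcome; significance level 0.05 (taken as two-sided). The protocol states no SD, correlation, effect size or power, so there is no figure of its own to reproduce.

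**Assumptions.** Pre-post correlation r = 0.3, 0.5, 0.7, 0.9; ratio k of post SD to pre SD of 1, with 1.25 and 0.75 as alternatives.

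**Step 1: identity.** On one simulated data set with 20 per arm, the group-by-time F was 1.6497 and the squared t on change was 1.6497.

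**Step 2: large-sample variances.** In units of the pre SD squared, per patient:

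- change contrast: 1 + k² − 2rk
- ANCOVA: k²(1 − r²)

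With k = 1 these are 2(1 − r) and 1 − r², so the SE ratio of change to ANCOVA is √(2/(1 + r)). This gives 1.240, 1.155, 1.085 and 1.026. The change contrast would need about 40 × 2/(1 + r) = 62, 53, 47 and 42 patients to match ANCOVA on 40.

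**Step 3: allowance for the small sample.** Estimating the slope multiplies the ANCOVA variance by about 1 + 1/(40 − 4) = 1.028. The two methods then have equal variance when (1 + r)/2 × 37/36 = 1, which is r = 0.946. Below that, with equal SDs, ANCOVA is the more precise.

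**Step 4: simulated ratio of mean 95% CI width, change over ANCOVA.**

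| Setting | r = 0.3 | r = 0.5 | r = 0.7 | r = 0.9 |
|---|---|---|---|---|
| 20 per arm, equal SDs | 1.222 | 1.137 | 1.070 | 1.012 |
| 16 per arm (20% loss assumed) | 1.219 | 1.133 | 1.063 | 1.008 |
| 20 per arm, ANCOVA also fits a two-level stratum that predicts nothing | 1.205 | 1.120 | 1.055 | 0.997 |
| 20 per arm, k = 1.25 | 1.114 | 1.042 | 0.996 | 1.012 |
| 20 per arm, k = 0.75 | 1.453 | 1.372 | 1.315 | 1.389 |
| Baseline cut at the population mean (HADS) | 1.077 | 1.044 | 1.017 | 0.996 |

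Nothing in the protocol supports either unequal SD ratio; those rows only show how far the result depends on it. In the HADS row, r is the correlation before the entry cut. With the cut 0.5 SD below or above the mean, the ratio at r = 0.5 is 1.063 or 1.029.

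**Step 5: closed-form checks.**

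- k = 1.25, r = 0.3: √(1.8125/1.4219) = 1.129, against 1.114 simulated.
- k = 0.75, r = 0.7: √(0.5125/0.2869) = 1.337, against 1.315.
- HADS cut at the mean, r = 0.5: a normal baseline keeps 0.363 of its variance, so √(1 + 0.363 × 0.5/1.5) = 1.059, against 1.044.

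The simulated values are slightly lower, as expected once ANCOVA pays for estimating the slope.

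**Step 6: validity.** Across the simulations at 20 per arm with equal SDs, type I error lay between 4.5% and 5.4% for both methods. Both recovered a true effect of 0.50 SD without bias.

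**The case against.** The strongest reply is that the protocol contains no error here. The planned test is valid, the clinical outcomes are secondary, no sample size rests on the test, and covariate adjustment is often left to an SAP. All but the last of these stand, and they set the weight of the point. The last does not remove it: the protocol names a specific method, and an SAP that used ANCOVA would depart from it.

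It is also fair that the gain cannot be fixed from the document. Across the scenarios it runs from nothing to 45%, and the upper end needs an SD ratio that the protocol does not support. For HADS the gain is small under every cut tried, and at r = 0.9 the planned analysis is marginally better. Nor does the protocol say how the later trial will use the steps/day data. If only the outcome SD or the dropout rate is taken forward, ANCOVA improves neither.

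Two further points concern the reading of the text. If Table 1's week 9 and week 10 marks for physical activity mean two separate post-programme assessments, the group-by-time test for steps/day has two numerator degrees of freedom and the identity does not apply. The calculation follows the Daily physical activity section, which describes one post-programme assessment. Also, the Statistical plan does not name the group-by-time term. If the group main effect were read instead, it would average pre and post and recover only half the effect (0.25 of 0.50 SD in simulation). That ambiguity favours a single adjusted contrast.

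**Conclusion.** The concern holds as a modest, nearly free improvement. The planned ANOVA is valid, but for steps/day, StGRQ and 6MWT it usually gives a wider interval than ANCOVA: about 22% to 7% wider for r from 0.3 to 0.7 with equal SDs and 20 per arm, and about 1% at r = 0.9. For HADS the difference is about 8% at most with the entry cut at the mean. The gain vanishes at r = 0.7 if the post SD is 1.25 times the pre SD. All these sizes rest on assumed correlations and SDs, and on one pre and one post value per outcome. No conclusion about adherence changes.

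**What to change.** In the Statistical plan, replace the repeated-measures ANOVA for steps/day, HADS, StGRQ and 6MWT with an ANCOVA of the post-programme value on arm, the baseline value of the same outcome and the 6MWT randomisation stratum. The stratum is optional when 6MWT is itself the outcome. The HADS stratum as printed cannot be used: entry already requires a score of 8 or above, so it takes one value for every patient. Report the adjusted mean difference with its 95% CI as the between-arm result. With two arms and one post-programme value there is a single contrast, so no post-hoc step is needed.

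For steps/day, use the single 7-day post-programme assessment described under Daily physical activity, and reconcile that section with the week 9 and week 10 marks in Table 1.

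The cost is wording and one or two degrees of freedom. The baseline values and the stratum are already collected. Even if the stratum predicts nothing, the advantage at 20 per arm with equal SDs is still about 20%, 12%, 5% and 0% across the four correlations.

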**Table 1: Assessment of variables prior to and following the rehabilitation programme**

Visit number (Assessments)	1	2	3	4
	Week 0	Week 1	Week 9	Week 10
Inclusion/Exclusion criteria	x			
Information & Informed consent	x			
Physical examination	x			
mMRC evaluation	x			
Current medication review	x			
Pulmonary Function Assessment		x		
Heart Function Assessment (resting ECG)		x		
BMI (body composition)		x		x
Oximetry & Blood Pressure		x		
6 Minute Walk Test		x		x
Daily Physical Activity Assessment	x		x	x
Quality of Life Assessment		x		x

**Figure 1: Study design** . PA: physical activity; CBM: cognitive behavioural modification, 6MWT: 6-min walk test, HADS: Hospital anxiety and depressions score, StGRQ: St’Georges Respiratory questionnaire.

**Figure 2: Consort Diagram.** PR: pulmonary rehabilitation, CBM: cognitive behavioural modification, PA: Physical activity promotion.

